11.3.1.16 Treatment and follow-up of adverse events

Participants with AEs that occur during the trial must be treated according to daily clinical practice at the discretion of the Investigator.

AEs must be followed up until resolution or to the end-of-trial visit, whichever comes first. At the end-of-trial visit, information on new AEs, if any, and stop dates for previously reported AEs must be recorded (if known). AEs assessed as stable by the Investigator at the end-of-trial visit will not have to be followed up until resolution.

It is the responsibility of the Investigator to follow-up on all SAEs until the participant has recovered, stabilised, or recovered with sequelae, and to report to the Sponsor all relevant new information using the same procedures and timelines as those for the initial report. Relevant information includes discharge summaries, autopsy reports, and medical consultations.

11.3.1.17 Procedures in case of pregnancy

In case of pregnancy or suspicion of possible pregnancy, the trial treatment must be stopped immediately, and the participant should be withdrawn from the trial.

Pregnancy itself will not be regarded as an AE unless there is a suspicion that the IMP may have interfered with the effectiveness of the contraceptive medication. However, the outcome of all pregnancies (spontaneous miscarriage, elective termination, normal birth or congenital abnormality) must be followed up by the Investigator and the Sponsor and documented even after the participant was discontinued from the trial.

All pregnancies must immediately be reported by the Investigator to the Sponsor or designee using the Pregnancy Report Form provided in the ISF. Once known, information on the outcome of the pregnancy must also be reported to the Sponsor or designee using the Pregnancy Report Form.

All events of congenital abnormalities, birth defects and spontaneous miscarriages are SAEs and must be handled and reported as such as described in Section 11.3.1.14.

Pregnancies in female partners of male trial participants should also be followed according to the procedures described above.

11.3.1.18 Medication errors and uses outside what is foreseen in the protocol

A medication error is an unintended failure in the drug treatment process that leads to or has the potential to lead to, harm to the participant.

Medication errors and uses outside what is foreseen in this protocol, including misuse and abuse of the product, will be reported in the participant's medical records, and documented in the protocol deviation (PD) log. Any medication error, misuse and/or abuse of the drug product will also be recorded in the AE log of the eCRF (refer to Section 11.3.1.8).

11.3.1.19 Treatment of overdose

An overdose is a dose in excess of the dose specified for each cohort in this CTP.

Overdosing is not likely to occur in this trial since all IMP will be administered by site personnel under medical surveillance. In cases of accidental overdose, standard supportive measures will be adopted as required.

Overdoses must be documented in the eCRF. An overdose with associated AE will be recorded as the AE diagnosis/symptoms in the AE log of the eCRF.

An overdose without associated symptoms will only be reported in the participant's medical records and documented in the PD log.

No known antidotes are available in case of overdose with GZ21T.

There have been no reported cases of GZ21T overdose.

11.3.2 Local tolerability

The Investigator will assess the incidence of local tolerability reactions of the administration site by direct inspection at visits and timepoints specified in Table 8.1-1 and Table 8.1-2 for Part A and in Table 8.1-3 for Part B. The assessment will include the Investigator's (or delegate's) evaluation of erythema, swelling, pruritus, burning and discoloration and dryness.

The presence/absence and intensity of local tolerability reactions at each time point will be recorded in a local tolerability module of the eCRF. Assessment of intensity will be performed as follows:

- Local tolerability reactions will be assessed by the Investigator or delegate as non, mild, moderate, or severe based on the definition of the reaction as outlined in Table 11.3-1. Discoloration is defined as change in skin tone other than erythema, *e.g.*, increased pigmentation or blanching, other than colour from the IMP. The intensity of each reaction will be documented in the eCRF.

Local tolerability reactions will be recorded as IMP-related AEs in the AE Log of the eCRF as follows:

- Erythema, swelling, pruritus, burning, blistering and urticaria: Grade 2 (moderate) and Grade 3 (severe) reactions **OR** Grade 1 if present \geq 24 hours after the start of IMP application.
- Dryness and discoloration: Grade 2 (moderate) and Grade 3 (severe) reactions.

As for other AEs, the full duration of the reaction(s), and the highest recorded intensity per reaction, should be entered.

Table 11.3-1 Local tolerability evaluation scale

Reaction	None=0	Mild=1	Moderate=2	Severe=3
Erythema	No detectable erythema; skin of normal colour	Slight pinkness present	Definite redness, easily recognised	Intense redness
Swelling	No swelling	Mild	Moderate	Severe
Pruritus	No pruritus	Occasional, slight itching/scratching	Constant or intermittent itching/scratching that is not disturbing sleep	Bothersome itching/scratching that is disturbing sleep
Burning	No burning	Slight warm, tingling sensation; not really bothersome	Definite warm, tingling sensation that is somewhat bothersome	Hot, tingling/stinging sensation that has caused definite discomfort
Blistering	None	Discrete signs	Moderate	Severe
Urticaria	None	Discrete signs	Moderate	Severe
Discoloration	None	Mild	Moderate	Severe
Dryness	None	Mild	Moderate	Severe

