2 If 1 participant on active treatment has an SAE assessed as at least possibly related to IMP administration.	
1. Stop dosing the participant with a potential SAR. Await the dosing of additional participants until the iSRC's recommendation and the Sponsor's decision on continuation.
 
2. Unblind the participant with potential SAR. Only voting members of the iSRC will be unblinded.
 
3. Evaluation by the iSRC. The iSRC makes a recommendation to the Sponsor.
 
4. The Sponsor decides how to proceed.
 
The participant received active treatment, i.e., met the stop criterion: stop further dosing at this dose level for all participants. The Sponsor decides if the trial will be terminated or if dosing will resume at a lower dose level.

3 If 2 participants on active treatment in the same cohort have severe, non-serious AEs assessed at least possibly related to the IMP administration (independent of whether the AEs are within the same system organ class [SOC]).	
1. Stop dosing the participants with severe, non-serious potential ARs.
 
2. Unblind the participants with potential ARs. Only voting members of the iSRC will be unblinded.
 
3. Evaluation by the iSRC. The iSRC makes a recommendation to the Sponsor.
 
4. The Sponsor decides how to proceed.
 
Both participants received active treatment, i.e., met the stop criterion: stop further dosing at this dose level for all participants. The Sponsor decides if the trial will be terminated or if dosing should resume at a lower dose level.

Final dosing stop and termination of trial	
4 If 2 participants on active treatment have SAEs assessed as at least possibly related to IMP administration.	
1. Stop dosing the participants with potential SARs. Await dosing additional participants until the iSRC's recommendation and the Sponsor's decision on continuation.
 
2. Unblind the participants with potential SARs. Only voting members of the iSRC will be unblinded.
 
3. Evaluation by the iSRC. The iSRC makes a recommendation to the Sponsor.
 
4. The Sponsor decides how to proceed.
 
Both participants received active treatment, i.e., met the stop criterion: Termination of trial.
 
One (1) participant received active treatment, i.e., met stop criterion: See stop criterion no. 2.

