11.2.10 Baseline symptoms

A baseline symptom is defined as an event that occurs between the participant's signing of the ICF and the administration of IMP (*i.e.*, an event that occurs during the screening period). Such events are not AEs and will be recorded as baseline symptoms in the AE log in the eCRF.

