11.3.1.6 Time period and frequency for collecting adverse events

All AEs (including SAEs) will be collected from the start of IMP administration until the end-of-trial visit.

Any AE with a start date on the day of the (first) IMP administration must be recorded with a start time.

At the end-of-trial visit, information on new AEs or SAEs, if any, and stop dates for ongoing events must be recorded as applicable.

Investigators will not be obliged to actively seek AEs or SAEs after the conclusion of the trial participation. However, if the Investigator learns of any SAE, including death, at any time after a participant has been discharged from the trial, and they consider the event to be reasonably related to the trial intervention or trial participation, the Investigator must promptly notify the Sponsor.

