11.3.1.11 Assessment of causal relationship

The Investigator must assess the causal relationship between an AE and the use of the IMP, using the definitions below. Each assessment should be recorded in the AE log of the eCRF.

Not related	There is no evidence of causal relationship with the IMP.
Unlikely related	The event has little evidence of causal relationship to the IMP.
Possible related	The event has a suggestive causal relationship to the IMP, and an alternative aetiology is equally or less likely.
Probable related	The event has a strong causal relationship to the IMP or recurs on re-challenge, and another aetiology is unlikely or significantly less likely.
Definitely related	The event is clearly related to the IMP.

An AE is considered causally related to the use of the IMP when the causality assessment is probable or possible.

11.3.1.12 *Outcome of adverse event*

The Investigator must assess the outcome of an AE using the definitions below and record it on the AE log of the eCRF.

Recovered/resolved	The participant has recovered completely, and no symptoms remain.
Recovering/resolving	The participant's condition is improving, but symptoms remain.
Recovered/resolved with sequelae	The participant has recovered, but some symptoms remain (e.g., the participant had a stroke and is functioning normally, but has some motor impairment).
Not recovered/not resolved	The participant's condition has not improved, and the symptoms are unchanged (e.g., atrial fibrillation has become chronic).
Fatal	
Unknown	

11.3.1.13 *Action taken with trial treatment*

The Investigator must document the action taken with trial treatment using the definitions below and record it on the AE log of the eCRF.

Dose increased N/A

Dose not changed

Dose reduced N/A

Drug interrupted

Drug withdrawn N/A

Not applicable

Unknown

11.3.1.14 *Reporting of serious adverse events*

The Investigator must report SAEs within **24 hours** of awareness to the Sponsor or its designee, this includes both initial information and any subsequent relevant/significant follow-up information to a previously reported SAE.

The primary mechanism for reporting an SAE will be via the eCRF. When the Investigator classifies the event as "serious" in the eCRF, and signs off the event, an automatic e-mail alert is sent to the Sponsor or its designee, and any other predefined recipients.

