10.2.2.2 Local tolerability

Table LT 1 Overview of local tolerability – Part A (Full analysis set)

												m
Any LT reaction graded higher than None	xx (xx%)	xx										
Any Erythema	xx (xx%)	xx										
Maximum grade Erythema												
None	xx (xx%)		xx (xx%)		xx (xx%)	xx	xx (xx%)		xx (xx%)	xx	xx (xx%)	
Mild	xx (xx%)		xx (xx%)		xx (xx%)	xx	xx (xx%)		xx (xx%)	xx	xx (xx%)	
Moderate	xx (xx%)		xx (xx%)		xx (xx%)	xx	xx (xx%)		xx (xx%)	xx	xx (xx%)	
Severe	xx (xx%)		xx (xx%)		xx (xx%)	xx	xx (xx%)		xx (xx%)	xx	xx (xx%)	
Any Swelling	xx (xx%)	xx										
Maximum grade Swelling												
None	xx (xx%)		xx (xx%)		xx (xx%)	xx	xx (xx%)		xx (xx%)	xx	xx (xx%)	
Mild	xx (xx%)		xx (xx%)		xx (xx%)	xx	xx (xx%)		xx (xx%)	xx	xx (xx%)	
Moderate	xx (xx%)		xx (xx%)		xx (xx%)	xx	xx (xx%)		xx (xx%)	xx	xx (xx%)	
Severe	xx (xx%)		xx (xx%)		xx (xx%)	xx	xx (xx%)		xx (xx%)	xx	xx (xx%)	
Any Pruritus	xx (xx%)	xx										
Maximum grade Pruritus												
None	xx (xx%)		xx (xx%)		xx (xx%)	xx	xx (xx%)		xx (xx%)	xx	xx (xx%)	
Mild	xx (xx%)		xx (xx%)		xx (xx%)	xx	xx (xx%)		xx (xx%)	xx	xx (xx%)	
Moderate	xx (xx%)		xx (xx%)		xx (xx%)	xx	xx (xx%)		xx (xx%)	xx	xx (xx%)	
Severe	xx (xx%)		xx (xx%)		xx (xx%)	xx	xx (xx%)		xx (xx%)	xx	xx (xx%)	
Any Burning	xx (xx%)	xx										
Maximum grade Burning												
None	xx (xx%)		xx (xx%)		xx (xx%)	xx	xx (xx%)		xx (xx%)	xx	xx (xx%)	

										m
Mild	xx (xx%)	xx (xx%)	xx (xx%)	xx	xx (xx%)	xx (xx%)	xx	xx (xx%)	xx	xx (xx%)
Moderate	xx (xx%)	xx (xx%)	xx (xx%)	xx	xx (xx%)	xx (xx%)	xx	xx (xx%)	xx	xx (xx%)
Severe	xx (xx%)	xx (xx%)	xx (xx%)	xx	xx (xx%)	xx (xx%)	xx	xx (xx%)	xx	xx (xx%)
Any Blistering	xx (xx%)	xx	xx (xx%)	xx	xx (xx%)	xx	xx	xx (xx%)	xx	xx (xx%)
Maximum grade Blistering										
None	xx (xx%)	xx (xx%)	xx (xx%)	xx	xx (xx%)	xx (xx%)	xx	xx (xx%)	xx	xx (xx%)
Mild	xx (xx%)	xx (xx%)	xx (xx%)	xx	xx (xx%)	xx (xx%)	xx	xx (xx%)	xx	xx (xx%)
Moderate	xx (xx%)	xx (xx%)	xx (xx%)	xx	xx (xx%)	xx (xx%)	xx	xx (xx%)	xx	xx (xx%)
Severe	xx (xx%)	xx (xx%)	xx (xx%)	xx	xx (xx%)	xx (xx%)	xx	xx (xx%)	xx	xx (xx%)
Any Urticaria	xx (xx%)	xx	xx (xx%)	xx	xx (xx%)	xx	xx	xx (xx%)	xx	xx (xx%)
Maximum grade Urticaria										
None	xx (xx%)	xx (xx%)	xx (xx%)	xx	xx (xx%)	xx (xx%)	xx	xx (xx%)	xx	xx (xx%)
Mild	xx (xx%)	xx (xx%)	xx (xx%)	xx	xx (xx%)	xx (xx%)	xx	xx (xx%)	xx	xx (xx%)
Moderate	xx (xx%)	xx (xx%)	xx (xx%)	xx	xx (xx%)	xx (xx%)	xx	xx (xx%)	xx	xx (xx%)
Severe	xx (xx%)	xx (xx%)	xx (xx%)	xx	xx (xx%)	xx (xx%)	xx	xx (xx%)	xx	xx (xx%)

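### Local reactions are counted, and recorded as IMP-related AEs, by absolute grade, so a sign present before dosing that persists unchanged can enter both counts

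*Protocol*

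**What the plan says.** Protocol section 11.3.2 turns local findings into AEs by rule: "Local tolerability reactions will be recorded as IMP-related AEs in the AE Log of the eCRF as follows". Two criteria follow. The first is "Erythema, swelling, pruritus, burning, blistering and urticaria: Grade 2 (moderate) and Grade 3 (severe) reactions", extended to Grade 1 of the same six reactions when present 24 hours or more after the start of application. The second is "Dryness and discoloration: Grade 2 (moderate) and Grade 3 (severe) reactions".

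Other sections bear on the same findings:

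- Section 11.2.10, on events between consent and dosing: "Such events are not AEs and will be recorded as baseline symptoms in the AE log in the eCRF".
- Section 11.3.1.6: "All AEs (including SAEs) will be collected from the start of IMP administration until the end-of-trial visit".
- Section 11.3.1.11: "The Investigator must assess the causal relationship between an AE and the use of the IMP, using the definitions below". The scale has five levels, and the lowest two are not related and unlikely related.
- Table 8.3-1, criterion 3, concerns two participants on active treatment in one cohort who "have severe, non-serious AEs assessed at least possibly related to the IMP administration".

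In the SAP, Tables LT 1 and LT 2 open with the row "Any LT reaction graded higher than None". They then give, for each reaction, a row for any occurrence and rows for the maximum grade. Neither SAP section 9.1.2 nor the table shells say whether pre-dose grades are left out. Tables LT 5 and LT 6 show shifts from baseline. Tables AE 7 and AE 8 select AEs by the recorded causality category.

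**The concern.** Local reactions and related AEs are primary safety outputs in Part A and are tabulated for Part B as well. A reader will take a count of reactions, or of related AEs, as a count of things that appeared or worsened after the cream was applied. The rule in section 11.3.2 and the shells of Tables LT 1-2 do not guarantee that, because an unchanged finding can satisfy both.

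The recorded causality is also unclear. One section fixes relatedness by rule and another asks for an individual judgement that may come out as not related. Section 11.3.2 does not say which of the three related categories to enter, although Tables AE 1 and AE 2 report each one. SAP Table 5 amends the definition of related by adding the definite category, but leaves this conflict open. The same label is used in Table 8.3-1, so the sections need to agree.

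**Working it through.** **Can an unchanged sign meet the rule?**

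1. Pre-dose is a local tolerability time point in Table 8.1-2 (Part A) and Table 8.1-4 (Part B). Section 11.3.2 records presence and intensity at each time point, and a shift from baseline is planned, so non-zero baselines are foreseen.
2. Take Grade 2 dryness before dosing and Grade 2 dryness at 24 hours. It meets the second criterion of section 11.3.2, and so would be an IMP-related AE. Under section 11.2.10 the pre-dose finding is a baseline symptom. Neither section says which prevails.
3. Take Grade 1 swelling or pruritus before dosing that is still present at 24 hours. It meets the 24-hour extension of the first criterion in the same way.
4. In Table LT 1 or LT 2, both examples count in the rows for any reaction and for maximum grade, since no restriction is stated. A Grade 1 dryness that never changes would count there too, although it never becomes an AE.
5. By comparison, sections 11.3.3, 11.3.4 and 11.3.6 limit AEs from vital signs, ECG and physical examination to abnormal findings after administration that the Investigator judges clinically significant. Section 11.3.2 has no such limit.

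**How large could it be?**

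There is no figure in the plan to reproduce and no stated background rate. Group sizes come from Protocol section 9.3: 4 × 6 = 24 active and 4 × 2 = 8 placebo in Part A (total 32, as stated), and up to 9 in Part B. Let p be the assumed chance that a participant has a qualifying sign before dosing that persists unchanged. Then the expected number is n × p, and the chance of at least one is 1 − (1 − p)^n.

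| Assumed p | Active: expected of 24 | At least 1 | Placebo: expected of 8 | At least 1 | Part B: expected of 9 | At least 1 |
|---|---|---|---|---|---|---|
| 1% | 0.24 | 21.4% | 0.08 | 7.7% | 0.09 | 8.6% |
| 5% | 1.2 | 70.8% | 0.4 | 33.7% | 0.45 | 37.0% |
| 10% | 2.4 | 92.0% | 0.8 | 57.0% | 0.9 | 61.3% |
| 20% | 4.8 | 99.5% | 1.6 | 83.2% | 1.8 | 86.6% |

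One affected participant is 1/6 = 16.7% of the active group in a Part A cohort and 1/3 = 33% of a Part B cohort.

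**Does it bias the comparison?** With the same p in both arms, the expected added proportion is p in each (for example 1.2/24 = 0.4/8 = 5%), so the added difference is p − p = 0. This treats persisting signs as additional to genuine reactions. Overlap within a participant could dilute a difference but not create one.

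**Criterion 3 of Table 8.3-1.** It needs at least 2 of 6 active participants in a cohort with severe events. At an assumed severe rate of 1% the chance per cohort is 0.15%; at 5% it is 3.3%.

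**The case against.** The opposing case has real weight.

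- AEs are collected only from dosing, and a local reaction can be read as a response to the application. On that reading pre-existing signs are excluded without saying so. This stands to the extent that a sign which resolves before dosing cannot become an AE. It does not settle the persisting sign, because section 11.3.2 uses the word reaction for findings at every time point, including pre-dose.
- The affected group is small. Exclusion criteria 6 to 9 remove people with skin conditions, urticaria or features of the skin that would interfere with assessment. Section 10.5 bars application to abraded, irritated or erythematous skin. Discoloration is defined as a change in skin tone, which is already relative, and mild dryness never becomes an AE. All this stands, and it is why dryness and mild swelling or pruritus are the main cases left.
- Baseline is already used in the shift tables. True for grades, but those tables do not correct Tables LT 1-2 or AE 7-8.
- Labelling threshold-level site reactions as related by rule is a legitimate conservative choice. This stands. The defect is that the choice is not reconciled with section 11.3.1.11, not that a rule is used.

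A reader might go further and infer that vehicle effects are labelled as drug effects and cannot be told apart. The documents do not support that for Part A: the placebo cream is itself one of the IMPs, reactions are recorded alike in both arms, and SAP section 9 presents a pooled placebo group. Only Part B has no comparator, and its sole listed endpoint in Table 7.1-2 is cream absorption.

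**Conclusion.** The point holds for absolute counts. As written, the plan allows an unchanged pre-dose sign to be reported as a local reaction and as an IMP-related AE, and sections 11.3.2, 11.2.10 and 11.3.1.11 give different answers for it. The size is unknown: the 1% to 20% range is an assumption with no source in the documents, and the screening and application rules argue for its lower part. Over that range the expected number is 0.24 to 4.8 of 24 active and 0.08 to 1.6 of 8 placebo participants. Part B is where it shows most, because cohorts have three participants and no placebo.

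Two stronger readings are not supported. The Part A active-placebo difference is not expected to be biased, given equal p in the two arms. Nor do the documents show that dose escalation would be misdirected: criterion 3 counts only severe events in participants on active treatment and goes through evaluation by the internal safety review committee. What they do show is that relatedness fixed by rule would enter a criterion worded in terms of assessment.

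**What to change.** **In the SAP**

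- Derive the rows for any reaction and maximum grade in Tables LT 1-2 from post-dose grades that exceed the participant's own pre-dose grade.
- In Tables AE 7-8, flag or show separately the local-reaction AEs that did not exceed the pre-dose grade.
- Keep the full counts alongside in both places, so nothing is hidden.
- State what happens when a pre-dose grade is missing. This matters for Part B: Table 8.1-4 marks local tolerability pre-dose, but the notes to Tables 8.1-3 and 8.1-4 name only dryness and discoloration at that time, so confirm that the other six reactions were graded.

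**Between the documents**

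Reconcile Protocol sections 11.3.2, 11.2.10 and 11.3.1.11 and the use of relatedness in Table 8.3-1. State whether causality is assigned by rule, and then in which category, or by the Investigator. No clinical or stopping rule is proposed here.

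**Cost**

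One added derivation and a footnote. The pre-dose grades are scheduled to be collected, and the SAP change works even if dosing is complete, as the SAP's past-tense account of randomisation suggests. The downside is a somewhat less conservative emergent count, which the full counts alongside offset.

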11.3.3 Vital signs

Systolic and diastolic blood pressure and pulse will be measured in a supine position after 10 minutes of rest.

Any vital signs outside of normal ranges will be judged as clinically significant or not clinically significant. The assessment will be recorded in the eCRF. Abnormal post-IMP administration findings assessed by the Investigator as clinically significant will be reported as AEs.

11.3.4 Electrocardiogram

Single 12-lead ECGs will be recorded in a supine position after 10 minutes of rest using an ECG machine. The resting heart rate and PQ/PR, QRS, QT and QTcF intervals will be recorded.

Safety ECGs will be reviewed and interpreted onsite by the Investigator.

Any abnormalities will be specified and documented as clinically significant or not clinically significant. Abnormal post-IMP administration findings assessed by the Investigator as clinically significant will be reported as AEs.

